#### 4.4 Recruitment and Screening

The PI or designee will screen the surgical schedule for eligible patients. This may include screening patients attending the preoperative clinic if the surgery is planned within three months. Because of the minimal interference to normal clinical care which this study

proposes, patients may also be invited to participate on the day of surgery, provided they receive this request on the ward before coming to theatre.

This is justified because there is even less knowledge currently about the management and outcomes of diabetic patients undergoing *emergency* surgery, who are acknowledged to be a particularly high-risk group, than diabetic patients undergoing elective surgery. Therefore, including a cohort of emergency surgery diabetic patients is particularly important to evaluate risk factors for adverse outcomes which may be mitigated. There is also anecdotal evidence that practice of managing these patients varies widely between nations and individual centres. The Surgical Outcome Risk Tool (SORT) will be used to indicate surgical risk [17]

#### 4.5 Methods of minimising bias

In every centre, all diabetic patients undergoing surgery, (except where there is only conscious sedation, with or without local anaesthetic infiltration or topical anaesthesia to the eye) are eligible. Centres are invited to enrol their target number of patients (depending on number of investigators in their team) from the date of registration of their centre with ESAIC and all approvals being in place, for up to 12 months. No other exclusion criteria apply, even emergency surgery patients are eligible. Therefore, we do not believe that significant risk of bias exists.

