### 4.2 Study centres and role of national and local PIs

Any hospital in Europe (as defined by the World Health Organisation) is welcome to participate as a study centre. Non-European centres may be accepted upon request to the SC. Centres will be asked to enrol a minimum of 45 patients (up to 200) over a recruitment period of up to 18 months from the date of the centre's registration with ESAIC. No more than one quarter (25%) of a centre's patients can be day cases (ambulatory anaesthesia). Study centre registration occurs online via the dedicated "Call for Centres form" on the ESAIC website. Within the overall Europe-wide period of recruitment planned for MOPED (at least 18 months), the start of recruitment for individual centres is soon as possible after centre registration with ESAIC, provided that there is prior IRB approval. Recruitment will continue until enrolment of the planned sample size (n=5,000).

National coordinating investigators are anaesthesiologists appointed by ESAIC and the SC to lead the project within individual countries and their responsibility includes:

- Identify centres in their country and recruit local PIs in participating hospitals;
- Assist in the translation of required study documents;
- Ensure that all necessary national or regional regulatory approvals are in place prior to start of patient inclusion;
- Assist and train the Local PI and monitor the conduct of the study according to ICH-GCP;
- Ensure good communication with ESAIC headquarters and the participating sites in his/her countries during all study steps including data cleaning.

Local PI may be anesthesiologists, surgeons or diabetes physicians working in perioperative medicine in each participating institution who will have the following responsibilities:

- Provide leadership for the study in their institution;
- Ensure all relevant regulatory/ethical approvals are in place for their institution;
- Ensure adequate training of all relevant staff prior to data collection;
- Supervise enrolment, daily data collection, and assist with problem solving;
- Adjudicate events
- Ensure timely completion of eCRF, follow-up assessments, and data cleaning queries. The Local PI is the main person responsible for ensuring integrity of data collection. By signing the data on eCRF Local PI confirms the data integrity;
- Communicate with ESAIC headquarters and the relevant National Coordinating Investigator during all study steps including data cleaning.

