## 6. PROJECT ASSESSMENTS

### 6.1 Project table of procedures and assessments: Figure 1.

PIs or designees will screen the elective surgical schedule for eligible patients. This may include screening patients attending the preoperative clinic if the surgery is planned within three months. The time window between answering the consent and surgery cannot exceed 90 days. Because of the minimal interference to normal clinical care which this study proposes, patients may also be invited to participate on the day of surgery, provided they receive this request on the ward before coming to theatre.

As it will also be particularly important to include diabetic patients undergoing emergency surgery, these patients will need to be screened and give informed consent on the day of surgery or up until to hospital discharge.

Intraoperative and postoperative management techniques of diabetes therapy will be documented, including capillary blood glucose levels before, during and <2hr after surgery. Also: Time to resumption of normal diabetes therapy (insulin or oral hypoglycaemics and diet); incidence of diabetic Ketoacidosis (defined as presence of the triad of: glucose > 12 mmol.L; ketonaemia > 3.0 mmol.L and lactaemia > 2.0 mmol.L; Incidence and duration of use of IV Insulin Infusion.

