## 7.3 Planned analyses

### 7.3.1 Main analysis

The aim of this research is to describe and quantify the epidemiology of the perioperative management of diabetic patients in Europe. Descriptive statistics such as mean (SD), median [interquartiles, range] and frequencies (%) will be presented as appropriate. The precision of the estimates will be reported with 95% confidence intervals to show the prevalence and incidence rates of diabetic phenotypes and major adverse events and complications.

The primary outcome measure is Days at Home at 30 Days (DAH-30).

Secondary outcomes include: Comprehensive Complications Index (CCI) score, based on Clavien-Dindo scale and the QoR-15 instrument measuring quality of recovery, taken only in patients who remain in hospital for Day 1 postoperative.

Secondary outcomes also include 30-day mortality, length of hospital stay, incidences of specific major adverse events (MI, MINS, AKI, PPC, CVA, PE, DVT and surgical site infection (SSI).)

Univariate analyses will be used to help identify variables of potential interest for multivariable analyses, in addition to stepwise selections. Robust multivariable regressions using maximum likelihood estimation (MLE), including Poisson and negative binomial, will be used to identify significant associations. Specific factors, or subsets of interest, will be investigated further using linear mixed models with MLE. Binary and categorical outcomes, such as occurrence of a postoperative pulmonary complication (PPC) will be analysed using multivariable logistic regression, survival analysis and Cox proportional hazards regression as appropriate.

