## 9. PUBLICATION AND DISSEMINATION POLICY

### 9.1 Publication of results

The main results of MOPED and its sub-studies will be published in peer-reviewed international medical journals and presented at Euroanaesthesia and at international and national meetings. As recommended by the International Committee of Medical Journal Editors (<http://www.icmje.org/recommendations/browse/roles-and-responsibilities/defining-the-role-of-authors-and-contributors.html>; accessed August 30th 2016), authorship will be considered based on contributions to recruitment of patients, data acquisition and cleaning, analysis and interpretation of the data, manuscript writing, and submission of national/local grants AND final approval of the version to be published AND agreement to be accountable for all aspects of the work in ensuring that questions related to the accuracy or integrity of any part of the work are appropriately investigated and resolved. The Steering Committee (SC) will also be the Writing Committee (WC).

All papers derived from the MOPED database will be published under the acronym "The MOPED Investigators". All authors will be specifically named, in order to give every investigator the same credit and the same responsibilities for successfully performing this study. All authors will be mentioned with their name and affiliation in the collaborators list which will be published in an appendix to the manuscript. The members of the Steering-

Writing committee will be specifically identified as required by most journals. Collaborators names will be listed in PubMed.

It is the responsibility of the local PIs to determine who is to be considered as investigator. The local PI will be asked to submit names of staff actively involved from their institution in the 'End of Study Reporting Form' (Appendix 17). If the number of recruited patients from a centre is too low to justify sufficient active involvement, the SC may decide on the legitimacy of the collaboration based on other contributions. The final decision will be left to the SC in consultation with the ESAIC.

The number of investigators allowed from each centre will be determined by the number of patients enrolled by that centre. This is described in Table 2 below.

Note that no more than 25% of a centre's enrolled patients should be day cases (ambulatory anaesthesia).

Table 2: Number of investigators named according to number of patients enrolled and followed to completion at 30 days:

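### Section 4.5 infers no significant bias from broad eligibility, but no rule says which eligible patients a centre must enrol, so the incidence estimates are open to selection of unknown direction and size

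*Protocol*

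**What the plan says.** Section 4.5 is the protocol's section on bias. Its argument has three steps:

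- Eligibility is wide: "No other exclusion criteria apply, even emergency surgery patients are eligible".
- The enrolment rule is a number: "Centres are invited to enrol their target number of patients (depending on number of investigators in their team", over up to 12 months.
- The conclusion: "Therefore, we do not believe that significant risk of bias exists".

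Other sections fill in the rule.

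- Section 4.2: "Centres will be asked to enrol a minimum of 45 patients (up to 200) over a recruitment period of up to 18 months". It also limits day cases to a quarter of a centre's patients.
- Section 9.1: "The number of investigators allowed from each centre will be determined by the number of patients enrolled by that centre". Table 2 gives 1, 2, 3 or 4 named investigators for 45, 85, 120 or 150 patients completed to day 30. Above 150 patients the limit is six names, and the centre maximum is 200 patients.
- Section 4.4: "The PI or designee will screen the surgical schedule for eligible patients".
- Section 2.4 says that listed elective and emergency patients will be approached and invited. It does not say all of them, or in what order.
- Section 6.4 has each centre report, at the end, how many patients met the inclusion criteria, how many were screening failures, and why.

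The main analysis in section 7.3.1 is descriptive, with 95% confidence intervals "to show the prevalence and incidence rates of diabetic phenotypes and major adverse events and complications".

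**The concern.** Eligibility criteria define the source population. The enrolment rule decides which members of it are observed. Section 4.5 gives a reason that concerns only the first and draws a conclusion about the second.

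This matters because estimation is the purpose of the study. Section 3.1 sets the incidence and severity of all complications to 30 days as an objective, and the synopsis asks whether management varies between centres and nations. If teams differ in whom they approach, part of any difference between centres reflects who was enrolled. A confidence interval does not cover that error, and a larger sample does not reduce it. How patients are sampled has to be fixed before enrolment, so it cannot be left to the analysis plan.

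**Working it through.** **1. Is there a rule on which patients to enrol?** The relevant sections, side by side:

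- 2.4: listed patients will be approached; no statement that all are, and no order.
- 4.4: the surgical schedule is screened; nothing on whom to approach from it.
- 4.5: a target number linked to team size.
- 4.2 and 9.1: minimum, maximum, day-case cap and authorship steps.

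None requires consecutive enrolment, approach of every eligible patient, random sampling or recruitment blocks fixed in advance. The one rule on case mix, the 25% day-case cap, makes the sample depart from the eligible population and so does not support 4.5 either.

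**2. How much room is there for selection?** The protocol gives no figure for this. The nearest is in the synopsis: 5% of 30 million operations = 1.5 million diabetic surgical patients a year, which reproduces. The same 5% can be applied to a single centre. Centre volume is not given, so it is an assumption, shown over a range.

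Enrolled fraction over 12 months = target / (0.05 × annual cases). The mean target is 5,000 / 50 = 100 at exactly 50 centres.

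| Assumed annual cases | Eligible | 45 patients | 100 patients | 200 patients |
|---|---|---|---|---|
| 2,000 | 100 | 45% | 100% | not reachable |
| 5,000 | 250 | 18% | 40% | 80% |
| 10,000 | 500 | 9% | 20% | 40% |
| 20,000 | 1,000 | 4.5% | 10% | 20% |

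A target of 100 is under half of the eligible patients only if 100 / (0.05 × V) < 0.5, that is V > 4,000 cases a year.

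**3. What could selection do to an incidence estimate?** Let p be the true risk, and let patients who will have the event be k times as likely to be enrolled as the others. Then

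- expected observed risk = kp / (kp + 1 − p)
- nominal 95% half-width = 1.96 × √(p(1 − p) / 5,000)

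Both p and k are assumptions.

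For p = 10% the half-width is 0.83 points.

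- k = 0.8: 0.08 / 0.98 = 8.2%, off by −1.84 points (2.2 half-widths)
- k = 0.9: 0.09 / 0.99 = 9.1%, off by −0.91 points (1.1 half-widths)
- k = 1.1: 0.11 / 1.01 = 10.9%, off by +0.89 points (1.1 half-widths)
- k = 1.25: 0.125 / 1.025 = 12.2%, off by +2.2 points (2.6 half-widths)

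For p = 2% the half-width is 0.39 points.

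- k = 0.8: 0.016 / 0.996 = 1.6% (1.0 half-width)
- k = 0.9: 0.018 / 0.998 = 1.8% (0.5 half-width)
- k = 1.1: 0.022 / 1.002 = 2.2% (0.5 half-width)
- k = 1.25: 0.025 / 1.005 = 2.5% (1.3 half-widths)

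The half-width assumes simple random sampling. Section 7.3.2 nests patients within centres, so the true interval is likely to be wider and these ratios smaller. At p = 10% and k = 0.8, clustering would have to multiply the variance by (1.84 / 0.83)² ≈ 4.9 before the half-width equalled the bias. At k = 0.9 a factor of (0.91 / 0.83)² ≈ 1.2 is enough.

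**The case against.** The best defence is that the protocol does more than 4.5 suggests. Section 2.4 has an approach rule covering elective and emergency patients. Section 6.4 makes the enrolled fraction visible and collects reasons for screening failure. The cap of 200 limits the weight of any one centre, and SORT describes surgical risk among those enrolled. All of this stands. But 2.4 does not say all or consecutive. The counts in 6.4 measure selection without preventing it, and that section describes no characteristics or outcomes of patients not enrolled.

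Some stronger readings are tempting, and the protocol does not support them.

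- *Centres hand-pick a minority.* No text tells centres to choose, and whether the enrolled are a minority depends on volumes the protocol does not give. At 2,000 cases a year, 100 patients would be all of them.
- *Emergency lists are not screened*, from 6.1: "PIs or designees will screen the elective surgical schedule for eligible patients". The next paragraph of 6.1 says that emergency patients need screening, 4.4 does not limit the schedule to elective cases, and Table 1 has an emergency screening entry on day 0.
- *Authorship credit favours easy patients.* Table 2 rewards number, not type. Follow-up is one 10-minute call, or ward collection for those still in hospital, so long-stay patients are not clearly harder to complete.
- *Reported risks will be too low.* Nothing in the protocol fixes the direction.

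**Conclusion.** The point holds as a correction to 4.5 and a low-cost improvement in design. The statement that no significant risk of bias exists is unsupported: its only premise is broad eligibility, the stated enrolment rule is a number tied to team size and authorship, and no section controls which eligible patients make up that number.

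The size is undetermined. Under the assumed values above, selection of 10% to 25% in either direction moves a 10% risk by 1.1 to 2.6 nominal half-widths, and a 2% risk by 0.5 to 1.3. Mild selection can therefore stay within the stated precision, and moderate selection need not. This shows that the risk cannot be dismissed. It does not show that the results will be biased, or which way.

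**What to change.** In 4.4 and 4.5, state that each centre:

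- declares its recruitment periods in advance, in whole weeks and not chosen weekdays, since operating lists may be organised by weekday;
- approaches every eligible elective and emergency patient whose surgery falls in those periods, consecutively by date of surgery (this keeps the order defined when elective consent is taken up to 90 days earlier);
- applies this separately to inpatients and day cases, with day-case enrolment stopping when the 25% cap is reached, until the centre's number is reached;
- reports eligible, approached, refused and enrolled counts for those periods.

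Replace the last sentence of 4.5 with a statement that selection is limited by consecutive enrolment and that residual selection will be described from these counts. If the sponsor prefers to keep the present sampling, that sentence should at least acknowledge the risk. The 12-month centre window in 4.5 and the 18-month window in 4.2 should be reconciled at the same time.

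Cost: protocol wording, a start and stop date per block, and two more counts on the end-of-study form if it does not already hold them. No extra patients or calls are needed. The downside is that work is bunched into blocks, at centres that receive no payment for recruitment. Emergency consent is already allowed up to discharge, so out-of-hours cover should not be needed.

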## 5. PROJECT POPULATION

### 5.1 Inclusion criteria:

- Diabetic patients 18 years or over (all classes except gestational diabetes) undergoing surgery (defined as requiring any general anaesthesia technique or any specific regional anaesthetic technique or a combination). Ambulatory, elective or emergency surgery and patients who receive postoperative care in intensive care or high dependency units will be included. Pre-defined subgroups of diabetic patients will be highlighted for later analysis.

### 5.2 Exclusion criteria:

- Patients who are not diabetic;
- Patients with gestational diabetes;
- Patients undergoing surgery without a specific anaesthetic technique, i.e. surgery under local anaesthetic infiltration or topical anaesthesia alone with or without monitored sedation alone or surgery not as defined in the inclusion criteria above.

Examples: Diabetic patient for cataract surgery. If anaesthetic technique will be simply topical anaesthesia, patient is excluded, whether or not there is monitored sedation.

If diabetic patient scheduled for cataract surgery with peribulbar or sub-tenon block, they are included.

### 5.3 Criteria for withdrawal / discontinuation of participants

Due to the observational nature of the study, the protocol does not define any withdrawal/discontinuation criteria. Patients electing to withdraw from the study may do so at any point. In this case, no further data will be collected, while already collected, encoded data will be pseudonymised and analysis may be performed up to the point of data collection. Withdrawing participants will not be replaced provided that their number does not exceed 5% of the projected sample size one month prior to the end of the planned recruitment period. Under such unlikely conditions, the SC will decide upon potential replacement by extension

of the recruitment period, under consideration (among other) of the number of events already registered in the database at the relevant time point.

## 6. PROJECT ASSESSMENTS

### 6.1 Project table of procedures and assessments: Figure 1.

PIs or designees will screen the elective surgical schedule for eligible patients. This may include screening patients attending the preoperative clinic if the surgery is planned within three months. The time window between answering the consent and surgery cannot exceed 90 days. Because of the minimal interference to normal clinical care which this study proposes, patients may also be invited to participate on the day of surgery, provided they receive this request on the ward before coming to theatre.

As it will also be particularly important to include diabetic patients undergoing emergency surgery, these patients will need to be screened and give informed consent on the day of surgery or up until to hospital discharge.

Intraoperative and postoperative management techniques of diabetes therapy will be documented, including capillary blood glucose levels before, during and <2hr after surgery. Also: Time to resumption of normal diabetes therapy (insulin or oral hypoglycaemics and diet); incidence of diabetic Ketoacidosis (defined as presence of the triad of: glucose > 12 mmol.L; ketonaemia > 3.0 mmol.L and lactaemia > 2.0 mmol.L; Incidence and duration of use of IV Insulin Infusion.

### 6.2 Assessments of primary endpoint outcome

The Primary Outcome is:

Days at Home at 30 days (DAH-30). [12,13].

Secondary Outcomes:

Comprehensive Complications Index [14,15]

The local Principal Investigators will determine the comprehensive complication index (CCI), based on the Clavien-Dindo scale based on review of in-hospital charts, other relevant documents, and questioning of patients. Appendix 11 gives the definitions of specific morbidity.[18]

How to calculate the CCI score for a patient is found in Appendix 14 'How to calculate the CCI score'

How to manage QoR-15 scale at Day 1:[16]. This is explained in Appendix 13 'QoR-15 Patient Survey'.

Investigators are asked to simply put the 15-point patient well-being questionnaire to the patient, if they remain in hospital on Day 1 only. This should be possible to achieve in 5 minutes.

The 15 domains of response are graded 0 (worst recovery) to 10 (best possible outcome). Therefore, given 15 responses, the range of QoR-15 scores is 0 to 150. Typically, values are skewed towards the higher end, typical median QoR scores are 100-120.

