#### 3.2 Primary and secondary endpoint/outcome(s)

Primary endpoint: Days at Home at 30 days (DAH-30) [12,13]

Secondary endpoints:

Comprehensive Complications Index (CCI) score, based on Clavien-Dindo scale; [14,15]

Quality of Recovery scale (QoR-15), only taken from patients who are in hospital the day after surgery, i.e. Day 1 postoperatively [16], 30-day mortality,

Length of Stay in Hospital, Length of Stay in ICU if applicable.

Incidence of specific major adverse events as listed in European Perioperative Clinical Outcomes Definitions manuscript[18], (see Appendix 11 'Definitions of Outcomes') (MI, MINS, AKI, PPC, CVA, PE, DVT, AKI, Postoperative pulmonary infection (PPI));

Tertiary end-Points:

Intraoperative and postoperative management techniques of diabetes therapy will be documented, including fasting capillary/ABG blood glucose levels before, and <3hr after surgery. Also, peak blood glucose recorded during surgery, if available.

Also: incidence of diabetic ketoacidosis (defined as presence of the triad of: glucose > 12 mmol.L; ketonaemia > 3.0 mmol.L and lactaemia > 2.0 mmol.L);

Incidence and duration of use of IV Insulin Infusion Therapy.  
Incidence of hypoglycaemia (glucose < 4 mmol/l or severe < 2,5 mmol/l).

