### 7.3.3 Handling of missing data

Analyses will be performed on the observed data. Data missing at random exceeding 10% may be imputed and models will be re-analysed as sensitivity analyses. Linear mixed models with MLE will be used as these are relatively robust with missing longitudinal data compared to least squares methods such as repeated measures analysis of variance (ANOVA). Exact multivariable logistic regression with Firth penalised MLE will be used for sparse and missing data as practical.

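### The planned missing-data methods do not suit QoR-15 scores missing because a Day 1 inpatient is too ill to answer; group comparisons are biased if that share differs between groups

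*Protocol*

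**What the plan says.** Section 3.2 lists QoR-15 as a secondary endpoint, "only taken from patients who are in hospital the day after surgery, i.e. Day 1 postoperatively". Section 6.2 sets the procedure: "Investigators are asked to simply put the 15-point patient well-being questionnaire to the patient, if they remain in hospital on Day 1 only". The patient grades 15 items from 0 to 10, so "given 15 responses, the range of QoR-15 scores is 0 to 150" with higher values better, and "typical median QoR scores are 100-120". There is one assessment, on Day 1.

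On who is enrolled, Section 5.1 states that "patients who receive postoperative care in intensive care or high dependency units will be included", and it also admits emergency surgery. Sections 3.1 and 7.3.4 compare outcomes by diabetes type, HbA1c stratum and anaesthetic technique.

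On missing data, Section 7.3.3 states: "Analyses will be performed on the observed data". It adds: "Data missing at random exceeding 10% may be imputed and models will be re-analysed as sensitivity analyses". It also names linear mixed models fitted by maximum likelihood, justified by their behaviour with longitudinal data, and exact logistic regression with Firth's penalty for sparse and missing data.

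On managing the questionnaire at Day 1, Section 6.2 says "This is explained in Appendix 13 'QoR-15 Patient Survey". That appendix is not in the text at hand. Nor are the case report form and its completion guidelines (Appendices 7 and 8), or any SAP.

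**The concern.** A patient who is in hospital on Day 1 but sedated, ventilated or delirious belongs to the population in which QoR-15 is defined and cannot supply a score. The score is absent because recovery is very poor. An analysis of observed scores drops these patients, so a group's mean is taken over those well enough to answer.

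If the share unable to answer is the same in both groups, the comparison is not distorted by this route. If it is higher in one group, that group looks better recovered than it was. For general versus regional anaesthesia an unequal share is plausible, since patients still sedated and ventilated on Day 1 would be expected mainly after general anaesthesia. For the HbA1c strata it is only an assumption. At stake is how the QoR-15 subgroup comparisons are read, not the primary endpoint.

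**Working it through.** **1. The plan's own benchmark.** Section 7.1 states at least 90% power for 0.15 SD with 5,000 patients at a Bonferroni level of 0.0007 (0.05/70 = 0.00071). For two groups of 2,500, two-sided: 0.15 × √(2500/2) = 5.30. The critical value is 3.39, and Φ(5.30 − 3.39) gives 97.2%. The statement is reproduced for equal groups, so 0.15 SD is used below as the yardstick. It refers to all 5,000 patients, whereas QoR-15 covers Day 1 inpatients only.

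**2. Does anything in Section 7.3.3 fit this case?**
- Observed-data analysis: leaves these patients out.
- Imputation: optional, a sensitivity analysis, and limited to data missing at random above 10%. Inability caused by poor recovery is not plausibly at random. Imputing from responders would tend to carry the bias forward.
- Linear mixed models: offered for longitudinal data, but QoR-15 is measured once.
- Firth-penalised logistic regression: concerns categorical outcomes, not a 0 to 150 score.

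None of the four addresses a once-measured score that is missing through illness.

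**3. Formula.** Let m be the share of a group's Day 1 inpatients unable to answer, μ the responder mean (taken as equal in both groups) and w the value given to those unable to answer. The mean over all Day 1 inpatients is (1 − m)μ + m·w = μ − m(μ − w). The observed difference is then 0, and the difference it hides is

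(m_B − m_A) × (μ − w), divided by the SD for standardised units.

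**4. Inputs.** μ = 110 is the middle of the medians of 100 to 120 in Section 6.2. The SD (20 to 30), the shares and w (0 or 50) are assumptions; the documents give none of them.

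| Unable to answer, A v B | Hidden difference, w = 0 | Hidden difference, w = 50 |
|---|---|---|
| 1% v 3% | 0.02 × 110 = 2.2 points (0.07–0.11 SD) | 0.02 × 60 = 1.2 points (0.04–0.06 SD) |
| 2% v 5% | 0.03 × 110 = 3.3 points (0.11–0.17 SD) | 0.03 × 60 = 1.8 points (0.06–0.09 SD) |
| 2% v 10% | 0.08 × 110 = 8.8 points (0.29–0.44 SD) | 0.08 × 60 = 4.8 points (0.16–0.24 SD) |
| 5% v 5% | 0 | 0 |

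Moving μ over 100 to 120 changes the 2% v 5% row to 3.0–3.6 points (w = 0) or 1.5–2.1 points (w = 50).

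**5. Gap that produces a bias of 0.15 SD.** Gap = 0.15 × SD / (μ − w).
- w = 0: 0.15 × 20/110 = 2.7 percentage points; 0.15 × 30/110 = 4.1.
- w = 50: 0.15 × 20/60 = 5.0 percentage points; 0.15 × 30/60 = 7.5.

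**The case against.** The strongest reply is that the rule may exist where it cannot be seen. Section 6.2 sends QoR-15 handling to Appendix 13, Section 6.4 refers to the eCRF for details, and a SAP often settles such matters. This stands for the reason field: the form may already have one. It does not remove the point about analysis, because Section 7.3.3 does not stay silent. It chooses an observed-data rule and names remedies, and none of them fits.

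Second, Section 7.3.1 plans multivariable regression, and SORT and ASA class are collected. Adjustment may absorb part of an imbalance in illness between groups, and the figures above are unadjusted. It does not remove the part of non-response that depends on recovery itself.

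Third, the size is assumed throughout, and the hidden difference depends on the score assigned to those who cannot answer. That stands.

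A reader might go further than the documents allow in these ways:
- **Deaths by Day 1 as lost scores.** Section 3.2 defines the endpoint in patients in hospital the day after surgery, so a patient already dead is outside it.
- **The worst outcomes vanish from the study.** They are absent from one questionnaire. DAH-30, CCI, 30-day mortality and ICU stay still capture enrolled patients.
- **A real disadvantage is reversed.** The working shows a difference hidden when responder means are equal; no reversal is shown.
- **Every missing emergency score means severe illness.** Sections 2.4 and 4.3 allow emergency consent until discharge, so some scores will be missing only because consent came after Day 1.

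Patients home before Day 1 are also outside the endpoint by design. They are probably the better recovered, so that restriction acts in the opposite direction if QoR-15 is read as describing all patients.

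**Conclusion.** The concern holds in a limited form. Section 7.3.3 fixes an observed-data main analysis for QoR-15, and its supplementary methods do not address inpatients too ill to answer. That non-response is informative, and it favours the group with more of it.

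Whether the bias is material depends on an unequal share unable to answer, which the documents do not give. Under the stated assumptions, a gap of roughly 3 to 4 percentage points (those unable counted as 0) or 5 to 7.5 (counted as 50) would match the 0.15 SD yardstick. Smaller gaps give less: 1% v 3% gives 0.04 to 0.11 SD. Equal shares give none. The effect is confined to one secondary endpoint, so this is a worthwhile improvement and not a threat to the main results.

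**What to change.** - **Record the reason.** For each Day 1 inpatient without a QoR-15, record one of: unable through illness (sedated, ventilated, delirious); consent obtained after Day 1; refusal, language or not asked. If Appendix 13 or the case report form already captures this, no new field is needed. If not, it should be recorded at the time, because a later SAP cannot reliably recover it.
- **Report the counts** of each reason by anaesthetic technique, HbA1c stratum and diabetes type.
- **Add one sensitivity analysis** beside the observed-data analysis: a rank-based comparison in which inability through illness takes the lowest rank. State that these records are not treated as missing at random.
- **Deaths before the Day 1 assessment:** report as counts by group, or rank lowest in the sensitivity analysis only, since they are outside the endpoint as defined.

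The cost is at most one form field and one extra analysis. The drawback is that the worst-rank result mixes inability to answer with poor recovery, so it supplements the observed-data result and does not replace it.
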